Participants will be randomly assigned to the esketamine group or placebo group at a 1:1 ratio. Randomization results will be achieved via a real-time, online system before surgery. A randomized four-blocks design stratified patients by depressive severity (severe depressive symptoms are defined by MADRS scores equal to or more than 30). The randomization sequence was created by independent engineers who will keep the allocation blind, and all study-related investigators will be blinded to the randomization results.

Intervention and anaesthesia management

All participants included in this study will receive trial drugs intravenously when the incision is being sutured. In the esketamine group, patients will be administered a total dose of 0.2 mg/kg esketamine (Hengrui Induction, Jiangsu, China) over 40 mins. Patients in the placebo group will receive an equivalent volume of normal saline at the same speed. Patients in this study will be under general anaesthesia for major surgery. Anaesthesia management will follow the standard procedure. Total intravenous anaesthesia or balanced anaesthesia will be implemented to maintain appropriate levels of sedation, analgesia, and muscle relaxation. Anaesthetics are administered at appropriate dosages based on consideration of the clinical anaesthetists and will include sedatives (propofol or etomidate), analgesics (sufentanil or remifentanil), muscle relaxants (rocuronium or cisatracurium), or inhaled anaesthetics (sevoflurane). Patient-controlled analgesia devices will be applied after surgery by using sufentanil and ondansetron to maintain numerical rating scale scores equal to or less than 4. Other analgesics could be used with the occurrence of severe pain (numerical rating scale score more than 7) during the postoperative period.

Blinding

The trial drugs will be prepared by an independent person who is not participating in screening, intervention, and follow-up procedures (see figure 2). Esketamine will be diluted to a concentration of 0.5 mg/ml with normal saline. Both esketamine and normal saline will be kept in syringes (50 ml) with the same appearance and labelled with "the trial drugs, randomization code". The participants will receive the trial drug at a speed of 0.6 ml/h per kilogram of weight for 40 min. The intervention will be completed by

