patients.²⁶ In the perioperative population with depressive symptoms, the remission rate was reported to be 23.1% in the ketamine group and 9.3% in the placebo group based on the PASSION study at our research site. We assumed that the remission rate in the esketamine group will be 19.3% and that in the placebo group will be 10%. A sample size of 506 participants will provide 80% power to show the difference between the esketamine group and the placebo group (with a ratio of 1:1), including 1 interim analysis by using a 2-sided significance level of 0.05.²⁷ With the consideration of a 10% attrition rate, the total sample size is planned to be 564.

Interim analysis

The planned interim analysis will be performed after 424 patients (75% of the total sample size) completed the follow-up. This interim analysis will be based on the ITT principle, and the P value will be set at 0.019 following adjustment by O'Brien-Fleming methods.²⁸

Statistical analysis

Continuous variables will be reported as the mean (standard deviation) for normally distributed data and the median (interquartile ranges) for skewed distributions. Categorical variables will be reported as the number (proportion), and the relative risk with its 95% confidence intervals will be calculated. The difference between groups will be reported with 95% confidence intervals of absolute differences calculated by independent t-tests for continuous variables and using the Hodges–Lehmann method for skewed variables. The primary endpoint of remission rate at 3 days after surgery will be analyzed by using the chi-square test or Fisher's exact test. The secondary outcomes will be analyzed using t-tests, Mann–Whitney U tests, and chi-square or Fisher's exact tests as appropriate. The adjusted odds ratios will be estimated by using a logistic regression model by taking into account the unbalanced baseline variables, age, sex, the severity of depressive symptoms, and pain severity after surgery.

For missing values, both imputations with the mean or median or the last observed assessment and multiple imputations will be applied. Sensitivity analysis for different imputation plans will be used to explore the statistical nature of the missing data. All statistical tests will be 2-sided at a significance level of 0.05 and the effect sizes will

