of 10 or greater for the initial diagnosis of depressive symptoms and a MADRS score of 22 or greater for the assessment of severity, with ages ranging from 18--65 years. Major surgeries, including neurosurgical tumor resection, coronary artery bypass grafting, total hip or knee arthroplasty, breast cancer surgery, pneumonectomy or hepatectomy, are estimated to exceed 2 hours. Participants who meet the exclusion criteria will be excluded. Patients who signed the informed consent will be randomized into the esketamine group or the placebo group. In the esketamine group, esketamine will begin to be administered intravenously at a total dose of 0.2 mg/kg per weight and will continue for 40 min. In the placebo group, the same volume of normal saline will be administered at the same infusion rate. All patients will be followed during the perioperative period for depressive symptoms and drug-related complications. The participants will be randomly assigned to the esketamine group or placebo group at a 1:1 ratio. Randomization results will be achieved via a real-time, online system before surgery. A randomized four-block design stratified patients by depressive severity (severe depressive symptoms are defined by MADRS scores equal to or greater than 30). The randomization sequence was created by independent engineers who will keep the allocation blinded, and all study-related investigators will be blinded to the randomization results. Randomization will be performed after informed written consent has been obtained.

Validation of endpoints

The data will be validated according to the prescribed rules. A research manager at each center will determine that all the data are complete, consistent and up-to-date. The research managers are also responsible for retrieving original data and checking and tracking the key endpoint data at the specified time.

Planned analyses

The detailed procedure of analysis in this SAP will be performed only after the database is frozen. The intent-to-treat and per-protocol populations will be determined before unblinding the treatment allocation.

Treatment comparisons

The comparison of interest in this trial is between esketamine and placebo administered intraoperatively over the 3-day period of depressive symptom remission after surgery.

4. Statistical hypotheses

The primary endpoint of this study is the remission rate 3 days after surgery in patients with moderate-to-severe depressive symptoms.

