The remission rate of depressive symptoms at 3 days postoperative will be summarized by treatment group via the chi-square test or Fisher's exact test to compare the differences between groups in the m-ITT population. The risk ratio for the intervention comparison is presented, and the 95% CI is reported. The results are

also displayed graphically on a histogram plot.

Secondary efficacy analysis

All secondary endpoints are based on the m-ITT population. For categorical variables, which are presented as frequency counts and percentages, a two-sided Pearson's χ^2 test or Fisher's exact test will be used, as appropriate. The odds ratios and 95% CIs were calculated. For continuous variables, prior to performing the statistical analysis, the assumptions of normality and homogeneity of variance of the residuals of quantitative variables were tested via the Shapiro-Wilk test and Levene's test, respectively. For efficacy analysis, a t test (normal variables) or the Mann-Whitney U test (skewed variables) will be used, as appropriate. The absolute difference and 95% CIs were calculated via the Mann-Whitney U test and the Hodges-Lehmann method.

Safety analysis

Safety endpoints will be assessed in the total population. The related variables are presented as frequency counts and percentages in both the esketamine group and the control group, odds ratios and 95% CIs.

Interaction with subgroups

A summary forest plot will be presented on the basis of the predefined subgroups, and interactions between them will be investigated for the primary endpoint. Exploratory subgroup-specific summary statistics and p values for interactions are presented. A separated logistic model was applied for interaction to identify its effect significance. The subgroup analysis included the following covariates: unbalanced baseline variables, age, sex, severity of depressive symptoms and pain severity after surgery.

Main results with Tables

Table 1. Demographic and preoperative characteristics of the total population.

Characteristics	Esketamine group	Control group
Sex		
Female	n (%)	n (%)
Male	n (%)	n (%)
Age, yr,	Mean (SD)/median (IQR)	Mean (SD)/median (IQR)
Height, cm,	Mean (SD)/median (IQR)	Mean (SD)/median (IQR)
Weight, kg,	Mean (SD)/median (IQR)	Mean (SD)/median (IQR)
Education	n (%)	n (%)
Married	n (%)	n (%)
Living state (alone)	n (%)	n (%)
Employed	n (%)	n (%)
Currently smoke	n (%)	n (%)
Alcohol intake		
Never	n (%)	n (%)
Occasional	n (%)	n (%)

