Patient-reported duration of illness		
< 1 month	n (%)	n (%)
1-3 months	n (%)	n (%)
Coexisting medical condition		
Diabetes	n (%)	n (%)
Hypertension	n (%)	n (%)
Stroke	n (%)	n (%)
Heart disease	n (%)	n (%)
Chronic pain	n (%)	n (%)
MDD	n (%)	n (%)
Motor dysfunction	n (%)	n (%)
Surgical history	n (%)	n (%)
ASA physical status	n (%)	n (%)
Charlson's comorbidity scores	Mean (SD)/median (IQR)	Mean (SD)/median (IQR)
Severe depressive symptoms	n (%)	n (%)
Recurrent malignancy	n (%)	n (%)
Preoperative assessment		
PHQ-9	Mean (SD)/median (IQR)	Mean (SD)/median (IQR)

MADRS	Mean (SD)/median (IQR)	Mean (SD)/median (IQR)
GAD-7	Mean (SD)/median (IQR)	Mean (SD)/median (IQR)
HADS	Mean (SD)/median (IQR)	Mean (SD)/median (IQR)
WHODAS 2.0 scores	Mean (SD)/median (IQR)	Mean (SD)/median (IQR)
Z-WHODAS 2.0	Mean (SD)/median (IQR)	Mean (SD)/median (IQR)
Type of surgery	n (%)	n (%)
Other ^a	n (%)	n (%)

Data are shown as the mean (SD)/median (interquartile range) and numbers (%).

Table 2. Primary outcome and Secondary outcomes.

Characteristics	Esketamine group	OR/Difference		P value
		Control group	(95%CI)	
Primary Outcome				
Remission on day 3	n (%)	n (%)	OR (95% CIs)	x
Secondary Outcomes				
NRS Pain scores >3, 0-48 Hours	n (%)	n (%)	OR (95% CIs)	x
Rescue analgesia, 0-48 Hours	n (%)	n (%)	OR (95% CIs)	x
Assessments on POD3				
MADRS	median (IQR)	median (IQR)	D (95% CIs)	x
GAD-7	median (IQR)	median (IQR)	D (95% CIs)	x
HADS	median (IQR)	median (IQR)	D (95% CIs)	x
PHQ-9≥10	n (%)	n (%)	OR (95% CIs)	x
Response	n (%)	n (%)	OR (95% CIs)	x
Assessments on discharge				
MADRS	median (IQR)	median (IQR)	D (95% CIs)	x
GAD-7	median (IQR)	median (IQR)	D (95% CIs)	x
HADS	median (IQR)	median (IQR)	D (95% CIs)	x
PHQ-9≥10	n (%)	n (%)	OR (95% CIs)	x
Response	n (%)	n (%)	OR (95% CIs)	x
Remission	n (%)	n (%)	OR (95% CIs)	x
Length of hospital stay	median (IQR)	median (IQR)	D (95% CIs)	x
Adverse events				
PONV, 0-48 Hours	n (%)	n (%)	OR (95% CIs)	x
Dissociative symptoms (CADSS≥5)	n (%)	n (%)	OR (95% CIs)	x
Psychotic side effects (BPRS 4 items≥5)	n (%)	n (%)	OR (95% CIs)	x
Manic symptoms (YMRS≥5)	n (%)	n (%)	OR (95% CIs)	x
Delirium	n (%)	n (%)	OR (95% CIs)	x
Infection after surgery	n (%)	n (%)	OR (95% CIs)	x
Bleeding events	n (%)	n (%)	OR (95% CIs)	x
Thrombus events	n (%)	n (%)	OR (95% CIs)	x

Figure 1 Flow chart and consort diagram of the study

Figure 2 Primary outcomes and MADRS scores

Figure 3 Subgroup analysis and interactions

10. Reference

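### The primary chi-square test ignores the randomisation stratum, the MADRS score tests ignore baseline MADRS, and the primary effect is a risk ratio in the text but an odds ratio in Table 2

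*SAP*

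**What the plan says.** **Randomisation.** Protocol, Randomization and grouping: "A randomized four-blocks design stratified patients by depressive severity". SAP section 3 has the same: "A randomized four-block design stratified patients by depressive severity". The cut is a MADRS score of 30.

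**Primary test.** Protocol, Statistical analysis: "The primary endpoint of remission rate at 3 days after surgery will be analyzed by using the chi-square test", with Fisher's exact test as the alternative. SAP section 9, Main Model: "The remission rate of depressive symptoms at 3 days postoperative will be summarized by treatment group via the chi-square test", again with Fisher as the alternative. Neither names the stratum.

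**Primary effect measure.** SAP section 4 states the hypothesis as a ratio of remission rates. The Main Model says "The risk ratio for the intervention comparison is presented, and the 95% CI is reported". The protocol says of categorical variables that "the relative risk with its 95% confidence intervals will be calculated". In SAP Table 2, however, the row "Remission on day 3" is set up to report an odds ratio.

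**Adjusted model.** The protocol adds a logistic model with "the unbalanced baseline variables, age, sex, the severity of depressive symptoms, and pain severity after surgery". In the SAP this covariate list appears only under the subgroup analysis.

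**MADRS scores.** SAP section 9 compares continuous secondary endpoints by t test or Mann-Whitney test with Hodges-Lehmann intervals, and Table 2 plans P values for MADRS on day 3 and at discharge. Linear regression is mentioned once, under the general calculations, with no covariate named. Both documents label the secondary endpoints exploratory.

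**The concern.** An analysis should normally reflect the randomisation. Stratifying balances severity between the arms and so removes between-stratum variation from the treatment comparison. An unstratified test still counts that variation as noise.

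The documents give a structural reason to expect severity to be prognostic. Remission is an absolute threshold of 10 or less and entry requires at least 22. A patient entering at 22 to 29 remits with a fall of 12 to 19 points, while a patient entering at 30 or more needs at least 20.

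The protocol's logistic model does not close the gap. It is supportive only. It conditions on pain after surgery, which is measured after treatment and may be affected by it, and on covariates picked for observed imbalance.

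What is at stake is a little power at the final analysis and at the interim look, where SAP section 6 lets the same comparison stop the trial; some precision in the MADRS scores; and an unsettled headline estimate, because the text and the results table name different measures.

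**Working it through.** **1. The plan's own figure.** Inputs from both sample size sections: p1 = 0.193, p2 = 0.10, two-sided 0.05, 80% power, one interim.

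- Pooled formula: n per arm = [1.960·√(2 × 0.1465 × 0.8535) + 0.842·√(0.193 × 0.807 + 0.10 × 0.90)]² / 0.093² = 226, or 452 in total.
- With continuity correction: 247 per arm, 494 in total.
- Times 1.028 for one O'Brien-Fleming-type look at 75% information: 508, against the stated 506.
- 506 / 0.9 = 562.2, so 563, or 564 as an even number.

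The sample size reproduces, and this point does not change it.

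**2. Why the unstratified test is conservative.** With stratum shares w and remission rates p, the pooled variance splits as P(1−P) = Σw·p(1−p) + Σw·(p−P)². With arms balanced by stratum, only the first term is real noise. Example with half the patients severe and null remission of 18% (moderate) and 2% (severe): 0.0900 = 0.0836 + 0.0064. The effective critical value is 1.96 / √(0.0836/0.0900) = 2.03, a type I error of about 4.2%. Simulation gives 4.1%.

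**3. Size at the final analysis.** The severe share and stratum rates are assumptions. Each scenario keeps the overall rates at 19.3% and 10%, with a common odds ratio within strata. Simulation: at least 1,000,000 trials per scenario, 253 per arm, nominal 5%, no interim adjustment; the stratified test is Cochran-Mantel-Haenszel (CMH) without continuity correction.

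| Severe share; placebo remission, moderate / severe | Stratum odds ratio | Type I error, chi-square / CMH | Power, chi-square / CMH |
|---|---|---|---|
| 50%; 18% / 2% | 10.8 | 4.13% / 4.98% | 86.3% / 88.5% |
| 50%; 17% / 3% | 6.6 | 4.28% / 4.95% | 85.9% / 87.6% |
| 50%; 15% / 5% | 3.4 | 4.57% / 4.94% | 85.5% / 86.2% |
| 20%; 11.5% / 4.1% | 3 | 4.79% / 4.99% | 85.1% / 85.4% |
| 30%; 11.6% / 6.2% | 2 | 4.83% / 4.96% | 85.1% / 85.2% |

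Stratum odds ratios are moderate against severe, for example (0.18/0.82)/(0.02/0.98) = 10.8.

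A second simulation used permuted blocks of four within stratum (506 patients, 400,000 trials per scenario, severe share 20% to 50%, stratum odds ratio 1 to 5). Chi-square type I error was 4.5% to 5.0%. The power gain was nil at an odds ratio of 1, 0.2 to 0.3 points at 2, and at most 1.4 points (85.6% to 87.0%) at 5 with half the patients severe.

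**4. Size at the interim.** 424 / 2 = 212 per arm, threshold 0.019.

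| Scenario | Null crossing, chi-square / CMH | Chance of crossing at planning rates, chi-square / CMH |
|---|---|---|
| 50%; 18% / 2% | 1.46% / 1.84% | 66.0% / 70.4% |
| 50%; 17% / 3% | 1.55% / 1.83% | 65.7% / 68.9% |
| 50%; 15% / 5% | 1.73% / 1.86% | 65.4% / 66.8% |
| 30%; 11.6% / 6.2% | 1.84% / 1.85% | 65.2% / 65.4% |

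**5. Risk ratio against odds ratio.** At the planning rates with 253 per arm:

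- Risk ratio = 0.193 / 0.10 = 1.93. SE of the log = √(0.807/(253 × 0.193) + 0.90/(253 × 0.10)) = 0.228; 95% CI about 1.23 to 3.02.
- Odds ratio = (0.193/0.807) / (0.10/0.90) = 2.15. SE of the log = √(1/(253 × 0.193 × 0.807) + 1/(253 × 0.10 × 0.90)) = 0.263; 95% CI about 1.28 to 3.61.

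**6. MADRS scores.** Adjusting for baseline multiplies residual variance by 1 − r². The documents give no correlation. At an assumed r of 0.3 to 0.5 the cut is 0.3² = 9% to 0.5² = 25%.

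**The case against.** The planned chi-square test is valid, is specified identically in both documents and keeps fixed-sample power above 80%, so a type I error slightly below 5% is not a defect. All of that stands: this is an efficiency point, not an error.

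The larger gains come from stratum odds ratios of 6.6 and 10.8 with half the patients severe, which nothing in the documents supports. That also stands. For odds ratios up to 5 the gain is 0 to 1.4 points.

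Severity is not wholly ignored: the protocol has the logistic model, and the SAP includes severity in the subgroup analysis of day-3 remission, with an interaction test. Neither is the primary test, so neither substitutes for stratifying it.

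The MADRS scores are exploratory, the entry threshold may lower the baseline correlation, and a variance cut for mean-based ANCOVA does not carry over directly to medians and Hodges-Lehmann differences. These limit the size of that gain, not its direction.

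On the effect measure, three places in the documents favour a ratio of rates, Table 2 is a shell, and the P value does not depend on the choice. So the correction is editorial. Still, the primary row contradicts the SAP's own text, and someone filling in the table would report the wrong measure.

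Finally, the SAP is labelled final, and changing the test after an interim look invites questions. This is a fair caution about timing. The simulated null crossing rates show that a chi-square look spends no more error than a stratified one, so a change made blind to results does not raise the error rate.

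**Conclusion.** The point holds on all three parts, at modest weight. The risk ratio/odds ratio conflict is a plain contradiction about the primary estimate (1.93 against 2.15 at the planning rates) and should be resolved. Ignoring the stratum does not threaten validity. It costs about 0.1 to 2 points of power at the final analysis and about 0.2 to 4.4 points in the chance of crossing at the interim, with the upper ends needing a very strongly prognostic stratum. If severity does not predict remission, the two tests perform alike. Leaving out baseline MADRS costs precision in exploratory endpoints only. These sizes rest on assumed severity shares, stratum effects and correlations. The final-analysis figures are at the nominal 5% level without adjustment for the interim look.

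**What to change.** Before unblinding, in the protocol and the SAP, and for the interim as well as the final analysis:

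- Make the primary test a Cochran-Mantel-Haenszel test stratified by randomisation severity (MADRS below 30 against 30 or more), with its exact version in place of Fisher's test if counts are small. Keep the unstratified chi-square as a sensitivity analysis.
- Report the Mantel-Haenszel risk ratio and risk difference with 95% confidence intervals in the text, and in Table 2 in place of the odds ratio for day-3 remission.
- Analyse the exploratory MADRS scores by ANCOVA on baseline MADRS, with robust standard errors, or by a rank-based version if skewed.
- If the interim has already been run with the chi-square test, record that look as done, and state that the change to the final test was made without sight of unblinded results.

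The cost is a documented change to the protocol's Statistical analysis section and to SAP sections 6 and 9, including Table 2. It needs no new data, visits or patients, because the stratum and baseline MADRS are already recorded. Correcting Table 2 alone is editorial and should be done even if the rest is declined.

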**Effect of esketamine on perioperative depressive symptoms
in major surgery patients (PASSION II)**

STUDY PROTOCOL

Protocol Version 2.0

Version Date: 20/01/2021

NCT number: NCT04425473

Prepared by statistician: [name]

Approved by Principal Investigator: [name]

Effect of esketamine on perioperative depressive symptoms in major surgery patients (PASSION II): study protocol for a randomized controlled trial

Introduction

Depression is a common mental disorder that has been the primary risk of disability and is an important risk factor associated with a high burden of disease; it is estimated that more than 300 million people suffer worldwide.¹⁻² Patients undergoing major surgery may have depressive symptoms induced by stress reactions, which could affect mental health in the surgery population. Depressive symptoms are characterized by loss of interest and low mood,—during the perioperative period. Although depressive symptoms are different from depression disorder, they could also lead to worse clinical outcomes after surgery, such as cognitive dysfunction, delirium, pain, and even shortened survival time.³⁻⁶ It has been reported that more than 24% of patients have depressive symptoms during the perioperative period, and this figure is nearly 44% in patients undergoing cardiac surgery or neurosurgery.⁶⁻⁹ However, few interventions resolve the depressive symptoms that occur during the perioperative period, and the influence of antidepressant effects in the early stage on prognosis in the future remains controversial.

Ketamine, a classic anaesthetic for sedation and analgesia, has been reported that could take rapid antidepressant effects in depression patients.¹⁰ However, the benefit of ketamine administration in patients with depressive symptoms undergoing major surgery is inconsistent.¹¹⁻¹³ To address this problem, our research team developed the PASSION study to explore the effect of ketamine on depressive symptoms in the neurosurgery population.¹⁴ In the 84 participants that were enrolled, we found that ketamine improved depressive symptoms at the third postoperative day, and the response rate was higher in the ketamine group than in the placebo group (41.5% vs. 16.3%), and no adverse events occurred. However, there were several limitations in the PASSION study; for example, the degree of remission did not reach desired levels chiefly because of the relatively small sample size, a single type of surgery was

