The safety of esketamine as an antidepressant in the context of surgery is unknown. Esketamine, as a novel drug for replacing ketamine, is not approved for intravenous use as an antidepressant. The plasma concentration for the antidepressant dosage of ketamine was reported to be approximately 70–200 ng/ml, which is far lower than the anaesthetic concentration (2000–3000 ng/ml).¹⁰ It is essential to explore an appropriate and safe dosage of esketamine for antidepressant treatment during surgery. Esketamine used in patients undergoing general anaesthesia is theoretically safer than the administration in awake patients. However, different anaesthetics administered during general anaesthesia may induce synergic effects with esketamine or attenuate treatment effectiveness. Thus, it is important to monitor the quality of recovery from general anaesthesia. Similar to ketamine, which could lead to psychotic symptoms, hallucinations, manic symptoms, or dissociative symptoms, esketamine given at an antidepressant dosage may also increase these risks after surgery. Determining the safe dosage will also be important for the popularization of esketamine used as an antidepressant during the perioperative period. Based on the previous study, both 0.2 mg/kg and 0.4 mg/kg of esketamine administrated intravenously were reported with remarkable anti-depression effects and low-dose of esketamine (0.2 mg/kg) with fewer side-effects rate than high-dose of esketamine after drug administration.¹⁵ Thus, we selected 0.2 mg/kg of esketamine as the intervention dosage in this study.

In summary, this study is a randomized controlled trial focusing on the mental health of perioperative patients. The expected result is that esketamine could markedly improve the remission rate after surgery without obvious adverse events, and long-term outcomes may also benefit from the administration of esketamine.

Footnotes

Funding: This study was supported by Beijing Municipal Science & Technology Commission (No. Z191100006619067) and Beijing Municipal Administration of Hospitals Clinical Medicine Development of Special Funding Support (DFL20180502).

Conflicts of interest: The authors declare no competing interests.

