If the amount of missing data is lower than the prescribed attrition rate, which is 10%, the data will drop out. Missing data during the assessment period will be replaced with negative results before breaking blind. Sensitivity analysis will be applied for the different imputation methods, such as imputation with means or medians or dropouts or negative results. The missing data will be reported and analysed to determine their effects on primary efficacy.

9. Statistical analysis

General statistical calculations

For binary outcomes, the summary statistics are reported as the number and proportion, and the χ^2 test was used for hypothesis testing. For outcomes measured on a continuous scale, the summary statistics are reported as the mean and standard deviation (SD) or median and interquartile range (IQR) depending on normality according to the Shapiro-Wilk test. Statistical inference to evaluate the effect of

treatment was presented as absolute mean differences and 95% CIs via the independent t test and linear regression for continuous variables, except skewed variables, for which the absolute difference and 95% CIs were calculated via the Mann-Whitney U test and the Hodges-Lehmann method. All the summarized descriptive statistics will be presented to one further decimal place unless otherwise specified. P values are rounded to 3 decimal places (those less than 0.001 are displayed as <0.001).

Follow-up data

The CONSORT flow chart will be used to summarize the follow-up of patients throughout the trial. Each center records the details of all randomization, intervention, and missing data.

Demographic and baseline characteristics

The demographic information, such as age, sex, weight, height, and body mass index, will be summarized and presented to the participants in the two intervention groups. Other variables included education level, marital status, American Society of Anesthesiologists physical status classification, Charlson's comorbidity index, smoking history, and comorbidity history. Baseline data for operation characteristics, such as delayed extubation, type and extent of resection, and time to spontaneous respiration, will also be obtained.

Efficacy analyses

All statistical analyses for the main effects were two-sided at P values less than 0.05.

Primary efficacy analysis

The primary outcome was postoperative 3-day remission events assessed by the MADRS scale after intervention.

Main Model

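### The SAP's only between-group safety estimate is the odds ratio, with no risk difference and no zero-cell rule, so the planned report may give no bound on excess risk for rare harms

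*SAP*

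**What the plan says.** SAP section 9, Safety analysis: "The related variables are presented as frequency counts and percentages in both the esketamine group and the control group, odds ratios and 95% CIs". In the Table 2 shell, all eight adverse-event rows (PONV, dissociative, psychotic and manic symptoms, delirium, infection, bleeding, thrombus) carry n (%) per arm, an odds ratio with 95% CI and a P value. The column is headed OR/Difference, but a difference is entered only on rows summarised by median and IQR.

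The general rules do not fill the gap:

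- SAP section 9, General statistical calculations: "For binary outcomes, the summary statistics are reported as the number and proportion", with a chi-square test. Absolute differences are for other variables: "absolute mean differences and 95% CIs via the independent t test and linear regression for continuous variables", with Hodges-Lehmann for skewed ones.
- Protocol, Statistical analysis: "Categorical variables will be reported as the number (proportion), and the relative risk with its 95% confidence intervals will be calculated". Its absolute differences are likewise tied to continuous and skewed variables.
- Fisher's exact test is mentioned for testing. No interval method, continuity correction or other rule is given for an odds ratio with an empty cell.

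For context, the protocol's Introduction says of the 84-patient pilot "and no adverse events occurred". The Discussion closes by expecting esketamine to "markedly improve the remission rate after surgery without obvious adverse events".

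**The concern.** Comparing harms is a stated objective of the SAP (section 2), and the protocol itself calls the safety of intraoperative esketamine unclear (Introduction) and unknown (Discussion). The useful safety result is how large an excess of each harm the data rule out.

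An odds ratio does not give that when events are rare. With no events in the placebo arm it is infinite and has no upper limit. With none in either arm it is undefined. With none in the esketamine arm it is 0, and whether it has an interval depends on a method the SAP does not name. The protocol's relative risk does not help, because it too is infinite or undefined when the placebo arm is empty. For such rows the finished table would show counts and an unusable comparison, leaving readers to work out the bound themselves.

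**Working it through.** **Inputs.** The documents state no expected harm rate, safety margin or target precision, so there is no safety figure to reproduce. The denominators come from the sample-size sections (Protocol; SAP section 5): 506 evaluable and 564 in total, allocated 1:1. Check: 506/0.9 = 562.2, or 563 rounded up and 564 as an even total. Arms are therefore 564/2 = 282 randomised or 506/2 = 253 evaluable. At the interim analysis they are 424/2 = 212. The harm rates below are assumptions, equal in both arms.

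**Step 1: how often an arm is empty.** P(no events in an arm) = (1 − r)^n. P(at least one empty arm) = 1 − [1 − (1 − r)^n]². For n = 282 and r = 0.5%: 0.995^282 = 0.243, and 1 − 0.757² = 0.427.

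| Assumed rate | Placebo arm empty, n = 282 | At least one arm empty, n = 282 | At least one arm empty, n = 253 |
|---|---|---|---|
| 0.2% | 57% | 81% | 84% |
| 0.5% | 24% | 43% | 48% |
| 1% | 6% | 11% | 15% |
| 2% | 0.3% | 0.7% | 1.2% |
| 5% | about 0 | about 0 | about 0 |

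The first probability column is the case in which the odds ratio has no upper limit. The problem matters for harms below about 1% and has practically gone at 2%.

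**Step 2: what each measure reports (282 per arm, esketamine versus placebo events).**

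| Events | Odds ratio (exact 95% CI) | Risk difference, points (Miettinen-Nurminen 95% CI) |
|---|---|---|
| 0 vs 0 | undefined (0 to infinity) | 0 (−1.35 to 1.35) |
| 1 vs 0 | infinite (0.03 to infinity) | 0.35 (−0.99 to 1.98) |
| 3 vs 0 | infinite (0.41 to infinity) | 1.06 (−0.29 to 3.08) |
| 5 vs 0 | infinite (0.92 to infinity) | 1.77 (0.41 to 4.09) |
| 3 vs 1 | 3.02 (0.24 to 159) | 0.71 (−1.01 to 2.77) |

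The Newcombe limits are close. For 0 vs 0 they are ±z²/(n + z²) = ±3.84/(282 + 3.84) = ±1.34 points. For 3 vs 0 they are −0.45 to 3.08.

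In the reverse case, 0 vs 3, the odds ratio is 0 and an exact interval has upper limit 1/0.414 = 2.4. That is finite, but it is not an absolute excess. The 3 vs 1 row shows that the odds ratio interval is hard to use even without an empty cell.

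**Step 3: sensitivity to the denominator.** For 0 vs 0 the bound is ±1.35 points at 282 per arm, ±1.50 at 253 and ±1.78 at 212. For 3 vs 0 the upper limit is 3.08 points at 282 and 3.43 at 253. The risk difference has a finite bound in every case.

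**Step 4: what the pilot shows.** Arm sizes are not stated; 41 and 43 fit the quoted response rates (17/41 = 41.5%, 7/43 = 16.3%) and are assumed here. The exact two-sided 95% upper limit for 0/41 is 1 − 0.025^(1/41) = 8.6%. The pilot's zero count therefore does not place any harm in the range where Step 1 matters.

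**The case against.** The strongest reply is that nothing is lost. Counts and percentages per arm are planned, and anyone can derive a risk difference and its interval from them. This stands against two stronger readings: that safety is summarised by odds ratios and P values alone, and that the trial is unable to bound excess risk. The SAP's own safety sentence contradicts the first, and Step 2 contradicts the second. What is missing is the planned reporting of the bound.

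Four further points also stand.

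- A reader might infer that non-significant P values will be taken as evidence of safety. No passage says so. The protocol's remark about adverse events is an expectation in its Discussion, not an analysis rule. The protocol treats secondary findings as exploratory, and SAP section 8 plans intervals without inferential tests for secondary endpoints.
- A reader might take the pilot as showing that these harms are rare. Step 4 shows it does not, and nothing in the documents suggests that PONV, delirium or infection are rare. The point concerns some Table 2 rows, not all.
- For 5 versus 0 it is tempting to set Fisher's P = 0.061 against a Newcombe interval that excludes zero (0.1 to 4.1 points). That contrast is mainly exact against asymptotic: the uncorrected chi-square is 564 × 5/559 = 5.04, P = 0.025.
- The SAP names no interval method for the odds ratio, so it cannot be faulted for a Wald interval. An exact one would give a lower limit for k versus 0, though still no upper limit.

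The reply does not meet the remaining gap: for the harms where a bound is most informative, the one comparison the SAP plans may not supply it.

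**Conclusion.** The point holds as a minor reporting improvement. The SAP's only between-group safety estimate is the odds ratio, no risk difference with an interval is planned for binary harms in either document, and no zero-cell rule is stated. For harms below about 1% the planned estimate has a material chance of being infinite or undefined (11% to 81% for at least one empty arm at assumed rates of 1% down to 0.2%, 282 per arm). The planned counts would support a bound of about ±1.3 to ±1.5 points when no events occur.

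This rests on assumed harm rates, equal in the two arms, and on 253 to 282 patients per arm. If a harm occurs in 2% or more of patients, empty cells are very unlikely and the gain is mainly readability.

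**What to change.** 1. In SAP section 9, Safety analysis, and in the Table 2 adverse-event rows, add the risk difference with a Newcombe or Miettinen-Nurminen 95% CI as the main between-group safety measure, and name the method chosen.
2. Show a ratio measure only where both arms have events, and say so in a table footnote. This serves as the zero-cell rule.
3. State that safety will be described by the interval, in particular by the excess it does not exclude, and not by non-significance.
4. Use one reconciled denominator of treated patients. SAP section 9 assesses safety in the total population, which section 7 defines as everyone screened with a record. Section 7 also assigns safety to the modified ITT population, which leaves out patients who cannot be followed because of surgical complications such as coma. The two passages must be reconciled before any risk difference is computed.

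The cost is one table column and a few sentences in the SAP. No new data are needed.
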